**Objective:** To determine whether KJD is non-inferior on patient reported effectiveness as compared to a KP (i.e. usual care) for relatively young patients with end-stage knee OA. In the GODIVA bone substudy, the primary objective is to predict the benefit from knee distraction treatment by peri-articular bone characteristics. The secondary objective of the substudy is understanding the change in peri-articular bone in relation to the benefit from knee distraction treatment (pain relief and cartilage repair) by expanding the pre-treatment data with follow-up data.

**Study design:** Pragmatic, open, randomized, multi-centre, non-inferiority trial with 24 months follow-up.

**Study population:** 1,200 knee OA patients  $\leq 65$  year of age, indicated for a KP will be randomized (1:1) to KJD or KP. For the GODIVA-bone substudy: 200 patients from the 600 patients randomised to treatment with knee distraction in the GODIVA trial will be included.

**Intervention (if applicable):** KP is indicated and surgically implanted according to regular clinical practice (can be a total- or unicompartmental KP, in line with local practice in consultation with the patient and conform the national guideline by Dutch orthopaedic society (NOV)). KJD treatment is performed according to the current approved concept NOV recommendations for clinical practice.

**Main study parameters/endpoints:** Primary endpoint: Western Ontario and McMaster Universities Arthritis Index (WOMAC) total score. Main secondary outcomes: WOMAC/KOOS Pain, stiffness, and physical function sub-scores, quality of life (EQ-5D, SF-36), radiographic joint space width (KJD only) as a surrogate for cartilage tissue repair; adverse events, and productivity and healthcare cost. All assessed over 24 months.

For the GODIVA-bone sub-study the main parameters are MRI, CT, and DEXA image markers and blood and urine biochemical markers at baseline and 24 months.

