### 3. STUDY DESIGN

Pragmatic, open, randomized, multi-centre, non-inferiority trial. 1,200 patients who satisfy the eligibility criteria will be randomized 1:1 to receive KJD or KP as initial treatment. These patients will be followed for 24 months. Both strategies will be implemented in regular care in participating centers taking current NOV practice recommendations for both treatments into account. In general study visits coincide with regular care although some visits are specific for the study and most outcome information is collected digitally via e-mail. Patients will be included over a period of 2 years.

**GODIVA-bone substudy:** The GODIVA trial provides an ideal platform to add specific measurements for bone (imaging and biochemical) before and two years after treatment to a subset of patients who will be treated with knee distraction (n=200).

At least 7-10 participating centers (together scheduled for over 200 knee distractions in the GODIVA trial) have been identified based on the availability of (access to) the right imaging equipment enabling the proper image acquisition and infrastructure for blood sampling and processing.

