#### 4.4 Sample size calculation

In the recently performed 'StWP' evaluation of KJD by 'Zorg Instituut Nederland (ZiN)' a non-inferiority limit for the 'crucial' endpoint of total WOMAC score at 2 years (the primary endpoint here) was defined at 15.

Assuming a 'true' difference in total WOMAC score of 12 points in favor of KP based on previous (pilot) data with an SD of 15 (14), 527 patients need to be recruited into each arm to obtain 90% power (2.5% one-sided significance) to demonstrate 'non-inferiority' (calculated using the power procedure in SAS 9.4). To account for missing data and loss to follow-up, we increase the sample size with ~15% and will include 600 patients per group.

**Sample size considerations for the GODIVA-bone substudy:** The response outcomes to use for the prediction models have an occurrence between ~30% and ~50%, indicating that with the 200 patients included (2/3 responder, i.e. 134 patients) we will have between 60 and 100 events for our analysis (between 40 and 67 for model development). Based on general rule of thumb, where at least 5-10 events per variable studies are needed we will have room for maximally 13 predictive parameters. To adhere to this, when needed, we will use data reduction techniques (e.g. principal component analysis or other feature reduction/selection techniques) or analysis techniques, suitable for sparse data, like penalized regression techniques to be defined in the SAP. For the secondary aim (explorative) we will relate changes in bone parameters to changes in pain (WOMAC pain) and cartilage tissue repair (radiographic joint space width increase) over a period of two years. The same parameters as explored in the predictive analysis as well as changes therein will be used as independent variables in this analysis.

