**In the second stage of the GODIVA-bone substudy**, bone parameters will be measured as continuous parameters, which is more time consuming but results in more sensitive measures. From radiographs, subchondral bone density and osteophyte size will be measured using KIDA software [Marijnissen A et al. Osteoarthr Cartil 2008;16,; Jansen M et al. Osteoarthr Cartil 2021;29,]. Bone mineral density will be measured from DEXA scans [Lo G et al. Semin Arthritis Rheum 2018;48,]. Subchondral bone density, cortical bone thickness and osteophyte volume will be measured from CT scans [Mastbergen S et al. Osteoarthr Cartil 2022;30,]. BML and cyst volume will be measured from MRI scans [Roemer F et al. Osteoarthr Cartil 2010;18,].

**In the third stage of the GODIVA-bone substudy**, image classification machine learning models (like convolutional neural networks) will be used for all imaging types to classify (in our case predict) which patients will be clinical and/or structural responders. These models can be used restricted (i.e. the model can only look at bone) and unrestricted. Available baseline images will be divided in training, validation, and test sets, to develop and confirm results of machine learning algorithms. At present we have gained experience in this approach by ML using images of PsA patients [Arbabi S et al. 2022; ms in preparation]. Final algorithms can not only be used directly for prediction; looking at which parts of the images are most important for the ML model provides additional information on which (bone) sites and properties are important for clinical and/or structural response and thus allow the definition of new features or combined selection of features from imaging to use in an overall prediction model (see below).

For biochemical data we will use serum/plasma samples and urine samples. When all baseline samples are collected, the state-of-the-art selection of bone biomarkers at that time will be made, together with experts in the field (Nordic Bioscience), and analysed (within feasibility with respect to costs).

Where relevant these results will be integrated with the endpoint analyses of the GODIVA trial.

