5. The clinical checks after surgery will be performed in line with local clinical practice. According to regular practice, patients treated with Knee prosthesis will visit the orthopaedic surgeon at ~6 and ~12 months after surgery for a clinical check. Patients treated with Knee Joint Distraction will visit the orthopaedic surgeon after ~3 weeks for a clinical check, at 6 weeks for removal of the distraction frame, and at ~6 months and at ~12 months after surgery for a clinical check. Although the clinic visits for check-up are not part of the study visits and follow regular care practice at the local center (and thus are not specifically depicted in above scheme), data on adverse events occurring will be specifically collected during the regular care visits in a standardized way (continuous registration, via standard notation in electronic health records and entered in Castor via EHR review). This is also the case for the standard measurement of knee flexion. Questionnaires will be sent to all participants via email (via Castor EDC) at 3 weeks and at 2, 5, 8, 12 and 24 months after surgery/start distraction period). At 12 and 24 months after surgery, only patients treated with joint distraction will be invited to come to the hospital for a radiograph of the knee (after 12 months is part of regular care according to NOV recommendations). At 24 months all patients will be contacted and asked if any additional surgical procedures of the knee have been performed or planned, which will be noted.

6. In case of early study termination, a phone call will be made to ask for the reason of termination and ask if any additional surgical procedures of the knee have been performed or planned.

**For the GODIVA-bone substudy:** Standard(ised) knee-MRI (single clinical time slot comprising 3 sequences), standard(ised) knee-CT, standard(ised) DEXA (according to the Imaging manual of the substudy), vena puncture for 2 times 7 cc blood and a urine sample will be collected at baseline and 2 years after treatment. Imaging and sampling will be performed as much as possible during the visits of the GODIVA study. Only for a limited number of patients extra visits may be needed.

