**GODIVA-bone substudy:** There is no direct benefit for the patient. Patients add to future well-balanced decision making by patient and surgeon together (shared decision-making) on whether to be treated with knee distraction or not, based on a scientifically justified chance for success of knee distraction treatment, is key for future implementation of knee distraction. Additionally, they will add to a more in-depth insight in the relationship between peri-articular bone changes and improvement in pain perception and cartilage repair, which may add to development and/or improvement of new and existing treatment strategies for knee osteoarthritis directed towards bone. Minimal risks are related to imaging procedures including radiation exposure by CT and DEXA imaging, as well as vena puncture. An indirect advantage is that for each patient a personalised feedback on the changes in bone parameters as a result of the treatment can be provided after end of the study.

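### GODIVA-bone substudy: the stated trigger has baseline bone biomarkers assayed before almost any 24-month sample exists, so run and plate differences can enter each patient's marker change (minor; exploratory aim)

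*Protocol*

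**What the plan says.** - **Trigger.** Protocol section 8.1.4 (biochemical data): "When all baseline samples are collected, the state-of-the-art selection of bone biomarkers at that time will be made". The same sentence continues, after mentioning outside experts, "and analysed (within feasibility with respect to costs". No other date for the assays appears in the protocol.
- **Sampling.** Section 8.3: "vena puncture for 2 times 7 cc blood and a urine sample will be collected at baseline and 2 years after treatment". The Summary counts "blood and urine biochemical markers at baseline and 24 months" among the main substudy parameters.
- **Calendar.** Section 3: "Patients will be included over a period of 2 years" and "These patients will be followed for 24 months". No separate inclusion period is given for the substudy.
- **Use of change.** Section 4.4, on the secondary substudy aim: "The same parameters as explored in the predictive analysis as well as changes therein will be used as independent variables in this analysis". Section 2 lists the relation of bone change to pain and cartilage repair as an objective. Sections 4.4 and 8.5 call this part exploratory.
- **Feedback.** Section 11.4: "for each patient a personalised feedback on the changes in bone parameters as a result of the treatment can be provided".

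The protocol does not mention pairing a patient's two samples in one run, reserving aliquots, or bridging between runs.

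**The concern.** The opening clause of the sentence in section 8.1.4 governs both the choice of markers and their analysis. A laboratory that follows it would assay all baseline samples about two years before the last follow-up samples arrive. Time point and assay run would then largely coincide. Each patient's marker change would be the biological change plus whatever differs between runs and plates (lots, calibration, drift), and the data could not separate the two.

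The substudy includes only patients treated with knee joint distraction, so no control arm could reveal or cancel a shift. Two quantities are exposed in different ways. The mean change over two years takes the full shift. The planned association of marker change with change in pain or joint space width is almost untouched by a shift common to everyone, but is weakened by error that differs from plate to plate.

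The timing matters because it may not be repairable. If baseline material is used up without a reserved aliquot, an analysis plan written before database lock cannot undo the run layout.

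**Working it through.** The plan gives no figure to reproduce on this point, so the check has two parts: the calendar, and the size of the effect under stated assumptions.

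**1. Calendar (document figures).** Inputs: inclusion A = 24 months and follow-up 24 months (section 3); baseline at most 2 months before surgery and a 24-month window of ±2 months (section 8.3 schedule); 200 patients (section 8.5). Assume uniform inclusion. With g the months from baseline to surgery and w the deviation of the visit, the share of 24-month samples in hand when the last baseline sample is drawn is

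share = max(0, (A − (24 + g + w)) / A).

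- A = 24, g = 0, w = 0: (24 − 24)/24 = 0%.
- Most favourable case, g = 0, w = −2: 2/24 = 8.3%, or 16.7 of 200.
- If inclusion overran to A = 30 (assumption): 2/30 to 8/30, 7% to 27%.
- If A = 36 (assumption): 8/36 to 14/36, 22% to 39%.
- About half is reached only near A = 48: 24/48 = 50% with g = w = 0.

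**2. Common shift: effect on mean change (assumed sizes).** Follow-up values are multiplied by k. SD of 2-year log change 0.2, 170 pairs.

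- Standard error = 0.2/√170 = 0.0153.
- k = 1.05: ln k = 0.049, or 3.2 standard errors.
- k = 1.10: ln k = 0.095, or 6.2 standard errors.
- k = 1.20: ln k = 0.182, or 11.9 standard errors.

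**3. Common shift: effect on the association (assumed sizes).** Raw units, baseline mean 3 and SD 1, true change SD 0.6, true correlation of marker change with outcome change 0.40.

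- Additive shift of 0.5 SD: mean change moves by 0.5 and the correlation stays at 0.40.
- k = 1.2: observed change = 1.2 × true change + 0.2 × baseline. Mean change moves by 0.2 × 3 = 0.6. SD of observed change = √(1.44 × 0.36 + 0.04 × 1) = 0.747. Covariance with the outcome (SD 1) = 1.2 × 0.40 × 0.6 = 0.288. Correlation = 0.288/0.747 = 0.385.

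**4. Plate-specific error: effect on the association (assumed sizes).** Log scale, true change SD 0.2, independent plate errors of SD s at the two time points. Observed correlation = 0.40 × 0.2/√(0.04 + 2s²).

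- s = 0.05: 0.40 × 0.2/√0.045 = 0.377.
- s = 0.10: 0.40 × 0.2/√0.060 = 0.327.
- s = 0.15: 0.40 × 0.2/√0.085 = 0.274. Simulation with a limited number of plates gives about 0.28.

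If both samples of a patient share a plate, a plate error that is multiplicative (additive on the log scale) cancels in the log change.

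**The case against.** **The text dates the selection, not the assay.** The words placing the choice at that moment attach to the selection, and the reference to analysis carries no date of its own. A sponsor could choose the panel then and assay stored pairs later without breaching the sentence. This stands in part. A reader might infer that the protocol prescribes separate follow-up runs; it does not. Separate runs are a consequence of the natural reading, and a laboratory manual could prevent them. Still, the opening clause governs both verbs, and no other timing rule exists.

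**Batch layout belongs in a laboratory manual or SAP.** Silence on plates would be no finding. The point here is the trigger that the protocol does state.

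**The planned analysis is hardly affected by a common shift.** This stands. A reader might infer from the 3 to 12 standard errors that the secondary aim is invalid. That figure concerns mean change, whereas the objective is an association. Section 4.4 also lets the parameters and their changes enter together. In an ordinary linear model with both, a multiplicative shift only rescales the coefficient of change and leaves its t-statistic unchanged. Plate-specific error is not covered by this argument.

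**Patients are promised feedback on their assay change.** A reader might infer this from section 11.4. The wording there is that feedback can be given. It concerns bone parameters, a term that section 8.1.4 uses for imaging measures, while the assays are called biomarkers. The documents do not support the stronger reading.

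**An early panel choice is a safeguard.** This stands. Choosing markers before most outcomes are known prevents an outcome-informed choice of predictors, so the selection should not be moved.

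**One baseline batch serves the primary substudy aim, prediction from baseline.** A single later assay campaign, with patients allocated to plates at random, also gives a complete set of baseline values in which plate is unrelated to response.

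**Conclusion.** The point holds as a minor, cheap improvement. On the stated calendar, 0% to 8% of the 24-month samples exist when the trigger in section 8.1.4 is reached, so following the text would put baseline and follow-up samples in different runs. Under assumed shifts of 5% to 20%, mean log change would be wrong by 0.049 to 0.182. The planned association would barely move under a common shift (0.40 to 0.385) and would weaken to between 0.38 and about 0.27 under assumed plate SDs of 0.05 to 0.15.

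The calendar result rests on uniform inclusion, and on substudy inclusion running as long as that of the main trial. The effect sizes are illustrations only, since the protocol gives no assay precision. The aim concerned is exploratory. The main trial is not affected, and the primary substudy aim uses baseline values only.

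**What to change.** Keep the selection of the marker panel at completion of baseline sampling. In section 8.1.4 change only the assay timing, for example:

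*Samples are stored frozen. After the last 24-month sample is collected, each patient's baseline and 24-month samples are assayed together in the same run and plate, in random order, with the laboratory blinded to time point and response. Baseline samples of patients without a 24-month sample are assayed in the same runs. If baseline samples are assayed earlier, a reserved aliquot is re-assayed with the 24-month sample for every change analysis.*

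**Cost.** A few sentences in the protocol or laboratory manual and no extra sampling. Baseline samples stay frozen longer and baseline values come later. This does not delay the prediction model if its response is the 24-month one, which is how section 10.3 is read here, although that section does not name the time point. The early-assay option additionally costs a second aliquot and a repeat assay. The change needs to be in place before baseline sampling is complete.

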## **8.2 Randomisation, blinding and treatment allocation**

After written informed consent has been obtained and patients fulfil the eligibility criteria they are randomised via the EDC system (Castor).

Randomisation will be performed centrally using blocked-randomisation (random block size) stratified by center and gender using the validated randomization unit from Castor ([www.castoredc.com](http://www.castoredc.com)). This is an unblinded study.

### 8.3 Study procedures

The following study assessments will be performed according to the schedule below.  
See appendices B-P for questionnaires.

	Screening/ Baseline	Pre- surg ery	Surg	Post-surgery								ET
				3w	6w	2m	5 m	8 m	12 m	24 m		
Weeks/ months	-2m (max)		0	+/- 1w	+/- 1w	+/- 2w	+/- 1m	+/- 1m	+/- 1m	+/- 2m		
Visits	V0			v1		v2	v3	v4	v5	v6		
General												
Informed consent	x											
In- and exclusion criteria	x											
Demographics/ characteristics	x											
Surgical medical history index knee	x											
Randomization		x										
Surgical treatment												
Knee prosthesis (KP) or Knee Joint Distraction (KJD) frame placement			x									
Removal KJD frame					x							
Questionnaires												
Pain Detect (neuropathic pain)	x											
KOOS (incl. pain medication)	x						x	x	x	x		
SF36	x								x	x		
EQ5D-5L	x			x		x	x	x	x	x		
NRS-Pain	x			x		x	x	x	x	x		
Patient Acceptable Symptom State	x						x		x	x		
NRS-Patient satisfaction							x		x	x		
Medical Consumption Quest. (MCQ)	x					x	x		x	x		
Productivity Cost Quest. (PCQ)	x					x	x		x	x		
Other												
Radiographic Joint space width (follow-up for KJD only) in mm **	x								x	x		
Adverse events/ additional surgical procedures *				x	x	x	x	x	x	x		
Knee flexion*	x			x	x	x	x	x	x	x		
Phone call											x	
GODIVA-bone substudy#												
Informed consent substudy	x											
In- and exclusion criteria substudy	x											
Image and biochemical markers for bone ##		x								x		

\* Adverse events / additional surgical procedures and knee flexion are specifically registered during regular care visits in a standardized way (continuous registration) so no study specific visits are planned for these measurements. Knee flexion is also measured at the baseline visit

\*\* Radiographs of the knee (according to KIDA protocol) for follow-up will only be taken after KJD (baseline X-ray for both KJD and KP). Only the 24-month x-ray is extra compared to KJD treatment in regular care according to preliminary NOV recommendations. Visits depicted in bold are study-specific clinic visits.

# only for patients treated with KJD

## only for patients participating in the GODIVA-bone substudy

1. At the study-specific baseline visit, after signing informed consent, in- and exclusion criteria will be formally checked. A radiograph of the knee is taken according to KIDA protocol (if a KIDA radiograph < 6 months is not available). This is in line with the KJD protocol for clinical practice recommended by the NOV (the Dutch orthopaedic society). If the patient is eligible, basic demographic and clinical information including the (limited) preference patients may have for any of the treatments is collected. In addition, questionnaires will be sent via email (via Castor EDC). When patients do not wish to receive digital questionnaires, they will receive paper versions by regular mail.
2. The patient will be randomized and will be informed about his/her allocated treatment (via phone or e-mail).
3. The patient will be invited for a pre-operative visit according to local clinical practice. During this visit, further details with respect to surgical and care practice (e.g. anesthesia) is provided in line with clinical practice in the respective centre. Surgery will be performed as soon as possible after this visit. Information about the techniques that are used for treatment (e.g. uni- or total prosthesis and type of distraction device), will be documented in Castor.
4. Surgery will be performed according to local clinical practice.
5. The clinical checks after surgery will be performed in line with local clinical practice. According to regular practice, patients treated with Knee prosthesis will visit the orthopaedic surgeon at ~6 and ~12 months after surgery for a clinical check. Patients treated with Knee Joint Distraction will visit the orthopaedic surgeon after ~3 weeks for a clinical check, at 6 weeks for removal of the distraction frame, and at ~6 months and at ~12 months after surgery for a clinical check. Although the clinic visits for check-up are not part of the study visits and follow regular care practice at the local center (and thus are not specifically depicted in above scheme), data on adverse events occurring will be specifically collected during the regular care visits in a standardized way (continuous registration, via standard notation in electronic health records and entered in Castor via EHR review). This is also the case for the standard measurement of knee flexion. Questionnaires will be sent to all participants via email (via Castor EDC) at 3 weeks and at 2, 5, 8, 12 and 24 months after surgery/start distraction period). At 12 and 24 months after surgery, only patients treated with joint distraction will be invited to come to the hospital for a radiograph of the knee (after 12 months is part of regular care according to NOV recommendations). At 24 months all patients will be contacted and asked if any additional surgical procedures of the knee have been performed or planned, which will be noted.

6. In case of early study termination, a phone call will be made to ask for the reason of termination and ask if any additional surgical procedures of the knee have been performed or planned.

**For the GODIVA-bone substudy:** Standard(ised) knee-MRI (single clinical time slot comprising 3 sequences), standard(ised) knee-CT, standard(ised) DEXA (according to the Imaging manual of the substudy), vena puncture for 2 times 7 cc blood and a urine sample will be collected at baseline and 2 years after treatment. Imaging and sampling will be performed as much as possible during the visits of the GODIVA study. Only for a limited number of patients extra visits may be needed.

